An *a priori* computer-generated stratified block randomization list will be used to assign patients to each of the 4 parallel fixed dosing schedules (allocation ratio 1:1:1:1, total subjects = 120). To ensure randomization of equal number of subjects to both nebulizers, block size of 8 will be used. To ensure equitable representation of gestational ages, GA stratum-specific randomization lists will be generated. Stratified block randomization will ensure balanced and independent distribution of participants within each dose group, avoid systematic differences between dose groups with respect to known or unknown confounding baseline variables, remove selection bias and control temporal trends^{2,62-66}. The balance resulting from blocked stratification can improve the power of trials by reducing unwanted variation, reduce Type I and II error rates, increase efficiency, and improve subgroup analyses.

The structure of Table 10 shows breakdown of the sample by confounding variables in rows (GA [stratifying factor] & nebulizer type [blocking factor]) with columns representing treatment groups. Therneau showed that balance in covariates begins to fail when the number of blocks approaches half the sample size (n/2)^{64,67}. Therefore studies using stratified assignment should not attempt to balance on

Table 10: Stratified Block Randomization of Sample

GA Group (Strata)	Nebulizer Device (Blocks)	Dosing Schedule			
		I	II	III	IV
24 0/7 – 28 6/7 (Extremely PT) ⁶¹	MiniHeart	5	5	5	5
	AeroNeb	5	5	5	5
29 0/7 – 32 6/7 (Very PT)	MiniHeart	5	5	5	5
	AeroNeb	5	5	5	5
33 0/7 – 36 6/7 (Moderately PT)	MiniHeart	5	5	5	5
	AeroNeb	5	5	5	5
Total		30	30	30	30

more than 2 to 3 important factors. In this study we have balanced 2 important factors (GA, nebulizer type); the resulting number of blocks (3 GA strata x 2 nebulizers x 4 dosing schedule groups=24) is <n/2 (120/2=60).

Multiple births, common in this premature population, will be randomized independently and not as a unit as the latter can lead to bias in the randomization process.

1.1.4.7. Allocation Concealment:

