Data will be analyzed according to the intention-to-treat principle using SAS and PASW (IBM Inc.). We will report descriptive statistics for demographic, clinical and respiratory support data at baseline and over time for the entire sample and for the 4 dosing schedule groups (Appendix IX [Table M1, M2]). In addition, three subgroup analyses are planned – according to dose regardless of dilution (100 vs. 200 mg/kg), GA strata, nebulizer device using logistic regression incorporating an additional treatment-by-subgroup interaction term.

Analysis plan to address Aim #1 – Safety and Feasibility Assessment: Safety will be assessed by quantifying and comparing the AEs and their severity for the total sample and across the dosage/dilution groups and two types of nebulizers. Indicators include cardiorespiratory responses, blockage of NIV circuit and cerebral oxygen saturation (Appendix IX [Table M5]). Descriptive statistics (mean, standard deviation, proportion, inter-quarter range [IQR]) will be used to quantify these indicators; *confidence intervals will be preferred to hypothesis testing* as considerable imprecision is expected arising from low frequencies of these AEs³. ANOVA or *t*-test (continuous measures) and χ^2 test (categorical variables) will be used for comparative analyses though we may not find statistically significant differences. Paired *t*-test will be used to compare heart rate, respiratory rate, blood pressure, SpO₂, PCO₂, cerebral oxygenation (RCO₂, cFTOE), ACoRN score and nasal exam score before and after AS. These parameters will also be compared between infants who get intubated within 72 hours of study intervention and those who do not; and before and after intubation within subjects that get intubated. Feasibility will be assessed by quantifying and comparing the percentage of infants who tolerate the treatment procedure and responses of the clinical nurses and respiratory therapists on the feasibility questionnaire (Appendix IX [Table M6]). Because of the high inherent variability of these factors and small effect sizes, we do not expect to show significant differences between groups given our sample size. However this information will be useful in making the final decision to proceed with a Phase III RCT.

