A number of secondary outcomes will be assessed using the same methodology. Vital signs, SpO₂, FiO₂, NIV parameters (pressure, rate, flow) and ABG/CBG components (pH, PO₂, PCO₂) will be evaluated before and after study intervention (paired *t*-test) and over time (Longitudinal data analysis). Other secondary outcomes include change in surfactant activity in gastric aspirates, changes in cerebral oxygenation, diagnosis of PDA, need for blood transfusions, postnatal growth, duration of respiratory support, length of hospital stay, and incidence of complications of prematurity including IVH, sepsis, NEC, BPD, pneumonia, ROP, and death. We will describe and compare primary and secondary outcome data overall and by dosing schedule, and in three pre-planned subgroup analyses – by dose regardless of dilution (100 mg/kg vs 200 mg/kg), GA group stratum and nebulizer type, recognizing that we may observe trends of differences between groups without having power to determine statistical significance. We will report dichotomous secondary outcome data as proportions and compare the groups using χ^2 and nonparametric tests. We will report secondary continuous outcome data as mean (SD) for normally distributed data and median (interquartile range [IQR]) for skewed data, and will compare the groups by using parametric (*t*-test, ANOVA) and nonparametric tests (Mann-Whitney U test, Wilcoxon's test) as appropriate. Pairwise group comparisons of the four dosing schedule groups will also be performed, although we may lack power to detect significant differences. In a final posthoc analysis, we will compare infants who received intubation within 72 hours to those who did not to understand risk factors for intubation and their modification by study intervention. This analysis will be presented for the entire group and by dosing schedule group. In *adjusted analyses*, dosing schedule, GA group, nebulizer type, mode of NIV, antenatal steroids, and presence of PDA or IVH will be included as covariates recognizing that these analyses are exploratory and need to be interpreted cautiously. We will consider a p value of <0.05 for statistical significance. Mock tables for the planned analyses are presented in Appendix IX.

Recommendations for statistical analyses by the Data Monitoring Committee (DMC) during the conduct of the trial:

1. Additional factors associated with intubation in enrolled infants – clinical team, time of day/shift, clinical variables (e.g. sepsis, NEC)

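### Randomization is stratified by gestational age and balanced by nebulizer, but the main between-schedule and between-dose comparisons do not condition on either factor

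*Combined protocol and SAP*

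**What the plan says.** **Design.** Section 1.1.4.6 sets four schedules ("allocation ratio 1:1:1:1, total subjects = 120"). For GA, "GA stratum-specific randomization lists will be generated"; for the device, "To ensure randomization of equal number of subjects to both nebulizers, block size of 8 will be used". Table 10 plans 10 infants per schedule in each of three GA strata, five on each nebulizer. The section gives the reason: "The balance resulting from blocked stratification can improve the power of trials by reducing unwanted variation, reduce Type I and II error rates".

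**Prognosis.** Sections 1.1.4.5 and 1.1.7.1 expect more intubation at lower GA, but no rate by stratum is given. Section 1.1.1 expects the choice of nebulizer not to affect efficacy, though it may affect feasibility.

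**Analysis (Section 1.1.12).**
- Aim #1, safety and feasibility: ANOVA or t-test for continuous measures and χ² for the rest ("categorical variables) will be used for comparative analyses though we may not find statistically significant differences"). Confidence intervals are preferred to tests because adverse events are expected to be infrequent.
- Secondary outcomes: "We will report dichotomous secondary outcome data as proportions and compare the groups using" χ² and nonparametric tests, with t-tests, ANOVA or rank tests for continuous data, and pairwise comparisons of the four schedules.
- Subgroups by dose, GA stratum and nebulizer: logistic regression with a treatment-by-subgroup interaction.
- Adjusted analyses: dosing schedule, GA group, nebulizer, mode of NIV, antenatal steroids, and PDA or IVH as covariates, "recognizing that these analyses are exploratory and need to be interpreted cautiously".
- Aim #3, efficacy: a one-sample comparison with the historical rate of 0.5.

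**The concern.** Stratified randomization makes the groups alike on GA. The true variance of a between-group difference then no longer contains the variation between strata. An unstratified χ², t-test or ANOVA still counts that variation in its standard error. When GA predicts outcome, the standard error is too large, the test rejects less often than 5% under the null, and the interval is too wide. The power that Section 1.1.4.6 cites as a reason for stratifying reaches the result only if the analysis conditions on the strata.

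This matters because finding a dose is a stated purpose of the trial, and Section 1.1.12 concedes several times that its group comparisons may lack power.

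The two places where GA and nebulizer do appear are not substitutes. An interaction term asks whether the effect differs between subgroups; it does not supply a stratified overall comparison of doses. The exploratory model names no outcome or model form. It also adjusts for PDA and IVH, which can follow randomization and are themselves secondary outcomes (Section 1.1.8), so its schedule effect is not a clean comparison of the groups as randomized.

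**Working it through.** **1. The plan's own power figure.** Table 13 concerns one group against 0.5. The arcsine formula is Φ(2·|asin√0.5 − asin√p|·√n − 1.96). With n = 30 and p = 0.25 it gives 81.8%, as stated. The other five rows give 98.2, 89.0, 99.99, 99.5 and 91.6%, against 98.2, 89.0, 99.9, 99.5 and 91.6% in the table. These figures involve no between-group comparison, so nothing below alters them.

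**2. Inputs for the dose comparison.** From the plan: three strata of 40, equal allocation, hence 60 v 60 with 20 per stratum per dose; two-sided 5% level. Assumed: intubation rates by stratum (lowest GA first) and a common odds ratio of 0.4.

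**3. Expected size of the unstratified test.** The ratio of the true variance to the variance that the test uses is

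R = mean of p_k(1 − p_k) ÷ [p̄(1 − p̄)],

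and the true size is 2·[1 − Φ(1.96/√R)].

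- Mild, 0.45/0.35/0.25: R = 0.2208/0.2275 = 0.971, size 4.7%.
- Moderate, 0.60/0.35/0.20: R = 0.2092/0.2364 = 0.885, size 3.7%.
- Steep, 0.80/0.40/0.10: R = 0.1633/0.2456 = 0.665, size 1.6%.

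The unstratified interval is too wide by a factor of about 1/√R: 1.01, 1.06 and 1.23.

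**4. Simulation.** Pearson χ² against the GA-stratified Cochran-Mantel-Haenszel (CMH) test, both without continuity correction, at least 100,000 trials per scenario:

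| Assumed rates | Size, unstratified v stratified | Power, unstratified v stratified |
|---|---|---|
| 0.45/0.35/0.25 | 4.7% v 4.9% | 57% v 57% |
| 0.60/0.35/0.20 | 3.7% v 5.0% | 54% v 57% |
| 0.80/0.40/0.10 | 1.7% v 5.0% | 35% v 50% |

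With no GA effect (0.35 throughout), power is 59% v 58%.

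**5. Enlarged sample.** Section 1.1.10 later allows up to 40 infants in the lowest stratum, 60 in each upper stratum, and 40 more across the upper two. If those 40 split evenly, the strata are 40/80/80 (n = 200). Power is then 73% v 76% (moderate) and 58% v 70% (steep).

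**6. All four schedules at once.** Three degrees of freedom, 30 per schedule, log-odds shifts assumed at 0, −0.5, −1.0 and −1.5. Power is 49% v 50% for 0.45/0.35/0.25, 40% v 47% for 0.60/0.30/0.15 and 27% v 44% for 0.75/0.30/0.10.

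**7. Infrequent adverse events.** With assumed rates of 10/4/1%, 60 v 60, size is 4.4% v 5.1% and power 11% v 12%.

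**8. Continuous outcomes.** If GA explains 5, 10 or 20% of the variance, the true size is 2·[1 − Φ(1.96/√(1 − R²))] = 4.4, 3.9 or 2.8%.

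**9. Point estimates.** The Mantel-Haenszel weight of a stratum is n₁n₀/(n₁ + n₀) = 20·20/40 = 10 in all three. With equal weights the stratified risk difference equals the crude one. The same holds for unequal strata as long as allocation within each is 1:1, because the weights are then proportional to stratum size.

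**The case against.** The strongest reply is that the plan already includes an adjusted analysis with GA and nebulizer, so a reader who infers that the benefit of stratifying is lost altogether goes too far. That is right: the gain is left to an exploratory analysis. What remains is that this analysis is ranked below the unstratified tests and mixes the design factors with PDA and IVH.

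Second, a reader might infer that the tests are too conservative as a matter of fact. The documents support the direction of the GA effect but not its steepness. With a mild gradient the two analyses have the same power, and with no gradient the unstratified test is about one point ahead. This stands, and it makes the concern conditional.

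Third, the quoted sentence on comparative tests belongs to safety and feasibility, where the plan prefers intervals and step 7 shows about one point of power at stake. This stands for infrequent events. Larger gains need outcomes that are common and strongly related to GA.

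Fourth, nebulizer is expected not to affect efficacy, so conditioning on it should add little for intubation. This also stands; its use is mainly for feasibility and device-related outcomes.

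Fifth, a conservative test creates no false positive findings, and the plan states openly that power is limited. Both are true, but neither is a reason to forgo precision that the design already provides.

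**Conclusion.** The concern holds in a limited form. The main between-schedule and 100 v 200 mg/kg comparisons do not condition on the randomization factors, and no analysis in the plan conditions on those factors alone. If GA is prognostic, these tests are conservative and their intervals too wide. For 60 v 60 at an odds ratio of 0.4, the power forgone runs from nothing (mild gradient) through about 3 points (moderate) to about 15 points (steep). All of these rest on assumed stratum rates.

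Two further inferences are not supported. The efficacy test against 0.5 and the powers in Table 13 are one-sample and are untouched. Nor would stratifying by GA change which schedule has the lowest observed rate: with balanced strata the crude risk differences stay the same and only p-values and interval widths change. This is a worthwhile gain in efficiency and does not threaten validity.

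**What to change.** In Section 1.1.12, name as the main between-schedule and between-dose comparison an analysis conditioned on the design factors only:

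- Binary outcomes: a GA-stratified Mantel-Haenszel risk difference with its confidence interval and a CMH test, or a logistic model with GA stratum reported as a standardised risk difference.
- Continuous outcomes: a linear model with GA stratum.
- Add nebulizer mainly for feasibility and device-related outcomes.
- Leave PDA and IVH out of this model. The wider covariate model can stay as exploratory, with its outcomes and form stated.
- Show the unstratified tests as secondary.

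The cost is SAP wording. GA stratum and nebulizer are already recorded for every infant, and no sample size changes.

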5. Serious abdominal, cardiac, airway or respiratory malformations including tracheal esophageal fistula, intestinal atresia, omphalocele, gastroschisis, pulmonary hypoplasia, or diaphragmatic hernia
6. Neuromuscular disorder resulting in respiratory compromise

1.1.4. Study Procedures:

Table 9: Time & Event Table:

Assessment	Screening	Baseline	Treatment	Post-intervention Events						
				0-24 hrs	0-24 hrs	0-24 hrs	0-72 hrs post intervention	D7	D14	D28
Informed consent	x									
History	x									
Vital Signs	x	x	x	x						
CRIB score		x								
RD score		x	x	x						
Nasal Trauma Score		x	x	x						
Blood gas	x	x	x	x						
Cerebral oximetry		x	x	x						
Gastric aspirate		x		x						
Effectiveness:										
Primary outcome				x						
Secondary outcome				x	x	x	x	x		x
Safety:										
Adverse events			x	x						

Feasibility:					X				
---------------------	--	--	--	--	---	--	--	--	--

CRIB-Clinical Risk Index for Babies; RD – respiratory distress; D7 = 7 days, D14 = 14 days, D28 = 28 days

Study procedures are described below and their time frame is summarized in Table 9; greater detail is provided in the *drafts* of the standard operating procedures (Appendix VII) and study forms (Appendix VIII).

1.1.4.1. Ascertainment of Study Eligibility:

Research staff will screen admission databases at HWH and CHM NICU for infants 24^{0/7} to 36^{6/7} weeks GA admitted at ≤ 24 hours of age for study eligibility and maintain a screening log. Informed parental consent will be sought for study participation of potentially eligible infants after a member of the clinical team obtains permission for research staff to approach the parent(s) (Appendix V). To minimize treatment delays, attempts will be made to obtain consent antenatally or soon after admission. Once the clinical team initiates NIV in a potentially eligible infant, the research team will determine that all inclusion criteria have been met, none of the exclusion criteria are present and fill out an Eligibility form. The infant will be assigned the next available pre-printed randomization number from the randomization log for the appropriate GA stratum. Research staff will determine the treatment assignment corresponding to the randomization number by calling the research pharmacy staff that is available 24/7. As confirmation of randomization, an order form documenting the randomization will be placed in the infant's electronic medical record (Appendix VII [Study Flow, Table A1]).

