Nasal trauma will be scored prior to AS, at end of AS and at 24 hours after AS^{53,81} (Appendix VII [Table A7])). At each time point, the nasal prongs will be briefly slid out of the nares and scores assigned for redness, bleeding, ulceration, or skin breakdown (Nasal Trauma Score) by research staff. In addition at the conclusion of the study intervention, the bedside nurse and respiratory therapist will complete a *Feasibility Questionnaire* to determine impact of study intervention on clinical care (Appendix VIII).

Ventilator parameters and vital signs will be monitored every 15 min during administration of aerosol, 30 min after completion of aerosol, every hourly till 4 hours and every 4 to 8 hour till 72h after completion of aerosol. CBG/ABGs are generally followed every 4 to 6 h for the first 24 h of life and every 4 to 12 h for the next 48 h, as clinically indicated and will be recorded. Cerebral oxygenation will be monitored before, during and after AS in all subjects. Demographic and clinical data will be collected prospectively. We will also record respiratory support at 3d, 7d, 14d, 28d and 36 weeks corrected GA; clinical course; need for medications (caffeine, pressors, sedation, indomethacin/ibuprofen, diuretics, postnatal steroids, antibiotics course, blood transfusions); morbidities; outcomes at discharge; and laboratory and imaging results.

1.1.4.11. Cerebral Oximetry Using Near Infrared Spectroscopy (NIRS):

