Participation in this part of the research protocol will be mandatory. Cerebral oxygen saturation (RCO₂) will be monitored before, during and after administration of AS using NIRS. Monitoring will be started once consent is obtained and will continue for 6 hours after end of last dose of AS. RCO₂ reflects oxygen saturation in veins (70–80%), capillaries (5%) and arteries (15–25%), and can be used as a surrogate for oxygen saturation in jugular venous blood^{82,83}. A near infrared spectrometer (Covidien®) will be used. A neonatal transducer, containing a light-emitting diode and two distant sensors, will be placed on the forehead in the midline. RCO₂ will be calculated from differential signals obtained from the two sensors, expressed as the venous-weighted percentage of oxygenated hemoglobin (oxygenated hemoglobin/total hemoglobin)⁸⁴. To investigate the balance between O₂ delivery and consumption, relative cerebral fractional tissue oxygen extraction (cFTOE) will be calculated as: $(\text{SaO}_2 - \text{RCO}_2)/\text{SaO}_2$ where SaO₂=arterial oxygen saturation⁸⁵.

1.1.4.12. Gastric Aspirates for quantitative PC analysis using LC-MS:

Parent(s) will be given an option for their infant's participation in this part of the study involving assessment of surfactant activity at baseline and end of AS in gastric aspirate samples. Surfactant activity will be determined by quantifying PC using LC-MS at the Lipidomics core at Wayne State University (Support letter from [name], Director Lipidomics Core attached). Baseline values will help us predict if an infant will respond to AS and levels after AS will help to assess efficacy of delivery and response to AS.

Gastric aspirates will be collected from eligible infants prior to starting AS and at the end of AS using a using an appropriate size nasogastric tube typically in place for routine clinical care. All samples will be assigned coded labels, frozen at –20°C and transported to the Lipidomics Core in batches for analyses.

1.1.5. Historical Controls:

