The Phase I/II Clinical Trial under this protocol does not have a placebo group; all randomized subjects receive active treatment. Preterm infants 24 0/7 - 36 6/7 weeks gestation that were admitted to the Hutzel Women's hospital NICU during the enrollment period (Dec 10, 2014 to Aug 31, 2017) will serve as historical controls to be able to compare intubation rates in infants enrolled and those not enrolled in the study. This will also allow comparison of other in-hospital outcomes, give an idea of numbers of infants available for the future Phase III clinical trial and the optimal time for administering study intervention.

1.1.6. Exit Criteria/Treatment Failure Criteria:

It will be suggested that infants be intubated and receive MV if they met 2 or more of 5 failure criteria:

- i). worsening clinical signs of respiratory distress (increasing tachypnea; expiratory grunting; intercostal, subcostal, and/or sternal recession);
- ii). apnea treated with positive pressure ventilation (PPV) by mask on 2 or more occasions in 1 hour;
- iii). FIO₂ >0.5 to maintain pulse oxygen saturations 90%-95% for >30 minutes;
- iv). pH <7.2 on 2 arterial or capillary blood gases taken >30 minutes apart; and
- v). partial pressure of CO₂ (PCO₂) of >65 mm Hg on 2 CBG/ABGs taken 30 minutes apart.

1.1.7. Primary outcome:

1.1.7.1. Safety:

Safety will be assessed by monitoring for oxygen desaturations, apnea, bradycardia/tachycardia, hypotension, air leaks, need for resuscitation, nasal trauma score, agitation, blockage of nasal prongs or NIV circuit, and cerebral oxygen saturation prior to, during and after study drug administration (Adverse Event [AE] Monitoring Form, Appendix VII [Table A8, A9]). Other safety measures that will be monitored include increased secretions requiring suctioning, coughing/gagging, surfactant reflux from nose/mouth, rainout in ventilator tubing, dislodged nasal prongs, abdominal distension, and nebulizer malfunction. It is expected that need for intubation is likely to be higher in the lower GA group strata.

1.1.7.2. Feasibility:

We define feasibility for this pilot RCT as the ability to:

- i). Safely deliver AS to PT infants with RDS without interrupting clinical care because of clogged nasal prongs or ventilator alarms related to inline nebulization. At the end of AS a Feasibility Questionnaire will be administered to bedside nurses & respiratory therapists to evaluate this (Appendix VIII).

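### Cerebral saturation during aerosol dosing is part of the primary safety outcome, but the only within-infant test around dosing is before versus after, which cannot show a fall that recovers

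*Combined protocol and SAP*

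**What the plan says.** Section 1.1.7.1 (Safety, under Primary outcome) includes "cerebral oxygen saturation prior to, during and after study drug administration". Of NIRS, section 1.1.4.11 says "Participation in this part of the research protocol will be mandatory" and "Monitoring will be started once consent is obtained and will continue for 6 hours after end of last dose of AS". Section 1.1.4.10 adds "Cerebral oxygenation will be monitored before, during and after AS in all subjects". In Table 9 the row "Cerebral oximetry" is marked at baseline, treatment and post-intervention.

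The analysis is in section 1.1.12. Under Aim #1, "Indicators include cardiorespiratory responses, blockage of NIV circuit and cerebral oxygen saturation", and "Descriptive statistics (mean, standard deviation, proportion, inter-quarter range [IQR]) will be used to quantify these indicators", with confidence intervals preferred to tests and comparisons across dosing groups and nebulizers. A paired t-test then covers a list of variables including RCO2 and ending "cFTOE), ACoRN score and nasal exam score before and after AS". The same variables are also compared between infants intubated within 72 hours and those not, and before versus after intubation.

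In the secondary-outcome paragraph, longitudinal analysis is named for vital signs, SpO2, FiO2, NIV settings and blood gases. Change in cerebral oxygenation appears in the next sentence, among other outcomes, with no time points. That paragraph also says that primary and secondary outcome data will be described and compared overall and by dosing schedule.

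**The concern.** The outcome definition has three periods and the paired test has two. The period left out is the exposure itself: the hours when prongs may block, aerosol is added to the circuit and the infant may be agitated. If cerebral oxygenation dips during nebulization and returns to its starting level afterwards, the before-after difference is close to zero and the test reads as reassuring.

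The adverse-event list in section 1.1.9 captures desaturation and apnea during dosing and for 6 hours after it, but does not identify these as cerebral. Section 1.1.4.11 describes RCO2 as mainly venous-weighted and introduces cFTOE to study the balance of oxygen delivery and consumption, so the protocol itself treats these measures as carrying information beyond SpO2. At stake is whether mandatory recordings made for a safety purpose are analyzed for the period they were meant to watch.

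**Working it through.** The documents give no sample size, power or effect size for cerebral saturation, so there is no figure of the plan's to reproduce.

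**1. Outcome against analysis**

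| Period | Outcome (1.1.7.1) | Recorded (1.1.4.10, 1.1.4.11, Table 9) | Paired test (1.1.12, Aim #1) |
|---|---|---|---|
| Before AS | yes | yes | yes |
| During AS | yes | yes | no |
| After AS | yes | yes | yes |

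The other contrasts named for RCO2 and cFTOE concern intubation and are not around dosing.

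**2. What the test can see.** Let B, D and A be an infant's values before, during and after AS. The test uses the mean of A − B. If the infant has recovered, A − B has expectation zero whatever D − B was, and the test rejects at its 5% level at any n.

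**3. Illustration of power.** The mean fall (5 saturation points) and the SD of the within-infant difference (5, 10 or 15) are assumptions. Paired t-test, two-sided 0.05, noncentral t with n − 1 degrees of freedom and noncentrality (δ/SD)·√n. Here δ = 0 after full recovery, 1.25 if a quarter of the fall remains, and 5 for before versus during.

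| n | SD | Before-after, full recovery | Before-after, 25% remains | Before-during |
|---|---|---|---|---|
| 30 | 5 | 0.05 | 0.26 | >0.99 |
| 30 | 10 | 0.05 | 0.10 | 0.75 |
| 30 | 15 | 0.05 | 0.07 | 0.42 |
| 120 | 5 | 0.05 | 0.78 | >0.99 |
| 120 | 10 | 0.05 | 0.27 | >0.99 |
| 120 | 15 | 0.05 | 0.15 | 0.95 |

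**4. Length of the omitted period.** Section 1.1.4.4 e) expects nebulization of one dose to take less than 1 hour in the smallest infants and less than 4 to 5 hours in the largest. NIRS continues 6 hours after the last dose. For one dose of d hours, the share of the record from the start of dosing is d/(d + 6): 1/7 = 14%, 4/10 = 40%, 5/11 = 45%. These are upper limits, and they leave out recording between consent and the first dose. They measure time, not harm.

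**5. Behaviour of candidate measures.** A during-AS mean dilutes brief falls: an assumed 15-point fall lasting 15 minutes in 4 hours moves the mean by 15 × 15/240 = 0.94 point. The lowest reading has the opposite problem. Assuming one normal reading per 15 minutes (the vital-sign interval in section 1.1.4.10), independence and no effect, the expected minimum is −1.03 SD for 4 readings (1 hour) and −1.63 SD for 12 (3 hours), a difference of 0.60 SD. Simulated with lag-one correlation 0.5 or 0.8, the difference is 0.65 or 0.58. Counts of infants with any fall depend on duration in the same way.

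Duration differs by schedule. Diluted volumes are 4 × 2 = 8, 4 × 3 = 12, 8 × 2 = 16 and 8 × 3 = 24 ml/kg on Schedules I to IV, a threefold range on a given device.

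**The case against.** The strongest reply is that the paired t-test is one item in Aim #1 and not its core. The core is description with confidence intervals plus comparison across groups; cerebral saturation is a named indicator there, and the outcome definition already includes the dosing period. The sentence on describing and comparing primary and secondary outcome data can be read as covering during-AS values. The Aim #1 indicator sentence points to Table M5 in Appendix IX, and the outcome definition points to Tables A8 and A9 in Appendix VII. None is in the public file, and any of them could hold a during-AS column or a graded cerebral event.

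Most of this stands. A reader might infer that during-AS cerebral data will go unanalyzed; the documents do not support that. What remains is narrower: the visible text gives no during-AS summary measure, and a proportion of a continuous saturation means nothing until an event is defined. The secondary-outcome paragraph opens by promising the same methodology, which might be stretched to bring cerebral oxygenation under longitudinal analysis, but the sentence naming that analysis lists its variables and omits it.

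A reader might also infer that the choice of schedule would be distorted, because Aim #2 favors the schedule with the fewest adverse responses. That is not shown. Aim #2 compares adverse responses, feasibility and outcomes across schedules and does not name the paired test as an input.

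Finally, a during-AS mean alone would partly share the defect, as step 5 of the working shows. That objection is right and shapes the fix.

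**Conclusion.** The point holds in a limited form. The plan names a within-infant contrast that omits the exposure period of its own safety outcome, and that contrast cannot detect a fall that recovers. The omission is confined to the cerebral measures: SpO2 desaturation, apnea, bradycardia and resuscitation during dosing are recorded as adverse events.

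No size can be put on the consequence, because the documents give neither the frequency nor the depth of cerebral falls; the power figures rest on assumed values and only illustrate the mechanism. The conclusion also assumes that the unseen tables do not already define a during-AS measure. It is a cheap improvement of minor severity, not evidence that safety is unmonitored or that the dose decision is unsound.

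**What to change.** In section 1.1.12, Aim #1, before the analysis is run:

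- Add a within-infant before-versus-during comparison of RCO2 and cFTOE for each dose given, using the infant's own mean before the first dose as baseline.
- Report the during-AS mean change together with measures that brief falls do not dilute: the number of infants with an RCO2 fall beyond a margin fixed in advance, and the minutes below it. For cFTOE the adverse direction is a rise.
- Show these beside nebulization time, with confidence intervals, by schedule, dose level and nebulizer.
- Keep the before-after test and say when its later reading is taken and after which dose, since section 1.1.4.4 d) allows two.
- If Table M5, A8 or A9 already defines a during-AS measure, cite and use it.

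The cost is SAP wording and programming on data already collected. A margin and an artefact rule must be set beforehand. The mean understates brief falls, while event counts, minutes below the margin and any minimum grow with nebulization time, so neither kind should be read alone. If only spot NIRS values were stored, minutes below the margin cannot be given and the lowest recorded during-AS value would have to serve.
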